7.2.5. Natural log (ACR)/eGFR

Baseline of natural log(ACR)/eGFR is defined as the ratio of the natural log of baseline ACR (defined in Section 7.2.4) divided by baseline eGFR (defined in Section 7.2.1).

7.3. Analysis Windows

Because clinical visits may occur outside protocol specified windows, instead of relying solely on visit labels in the clinical database, analysis visits and their windows are defined using Study Day (See Section 7.1.2). Analysis visit windows are presented in Table 3 by type of assessments and/or measurements.

If more than one on-treatment assessments and/or measurements exists for a parameter within a visit window, the one that is closest to the protocol scheduled time point (or target Study Day) will be used for analysis and summary. If more than one off-treatment assessment exists, the one closest to the target study day will be used for analysis and summary.

Table 3: Analysis Windows

Visit Scheduled Time Point	Target Study Day	Analysis Visit Windows	
		All Other Assessments	12-lead ECG
Screen A	-60	-180 to -2	-180 to 1
Screen B ^a	-1	-30 to -1	-
Day 1	1	1	-
Week 1	7	2 to 10	-
Week 2	14	11 to 21	-
Week 4	28	22 to 35	-
Week 6	42	36 to 49	-
Week 8	56	50 to 70	-
Week 12	84	71 to 98	2 to 98
Week 16	112	> 98	-

^aScreen B is after Screen A, and no more than 30 days prior to Day 1

Note: Study Day is relative to the first date of study drug administration (Study Day 1). Visit Scheduled Time Point = Analysis Visit (AVISIT), after applying the analysis windows described above. The Week 16 visit has the additional restriction that assessments must be collected after last dose of study treatment. For patients who terminated treatment prior to Week 12, use Week 16 as follow-up visit.

If more than one measurement is collected equidistant to the target Study Day and on different collection date/time, the first measurement will be flagged for analysis and summary. If more than one measurement is closest to the target Study Day and collected on the same date, the average of those measurements will be used for analysis and summary.

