#### 7.5. Schedule of Assessments

Table 5 lists the overall schedule of assessments for the study.

Table 5: Schedule of Assessments

Assessment	Screen A a	Screen B b	Day 1°	Wk 1 (Phone) Day 3±2	Wk 1 Day 7±3	Wk 2 (Phone) Day 10±2	Wk 2 Day 14±3	Wk 3 (Phone) Day 21±2	Wk 4 Day 28±3	Wk 4 (Phone) Day 31±2	Wk 5 (Phone) Day 38±2	Wk 6 Day 42±3	Wk 7 (Phone) Day 45±2	Wk 8 Day 56±3	Wk 12 or EoT d Day 84±3	Wk 16 or F/U Day 112±3
Informed consent	X															
Inclusion/ exclusion	X		Χ°													
Demographics and baseline disease characteristics	X															
Concomitant medications	X	X	X	X	X	X	X	X	X	X	X	X	X	X	X	X
Medical history	X															
Height	X															
Weight in clinic/BMI	X		X		X		X		X			X		X	X	X
Weight at home			X	X	X	X	X	X	X	X	X	X	X	X	X	
Dispense weight diary			X				X		X			X		X		
Collect/review weight diary				X	X	X	X	X	X	X	X	X	X	X	X	
ECG	X														X	X
Echocardiogram f	X															
Vital sign measurements	X		X		X		X		X			X		X	X	X
Physical exam	X		X		X		X		X			X		X	X	X
Pregnancy test for WOCBPs	X	X	X						X					X	X	X
Study drug administration									Х	ζ			_			
Dispense study drug			X				X		X			X		X		
Collect study drug							X		X			X		X	X	
Telephone contact				X		X		X		X	X		X			
Adverse event collection			Xh	X	X	X	X	X	X	X	X	X	X	X	X	X
Kidney biopsyi	X															
Fasting C-peptide level j	X															
Genetic testing k	X															
Clinical chemistry (incl. eGFR)	X	X	X		X		X		X			X		X	X	X
BNP and NT-proBNP	X		X		X		X		X			X		X	X	X
IGF-1 and serum ketones	X		X		X		X		X			X		X	X	X
Hematology	X		X				X		X			X		X	X	X
Urinalysis and microscopy	X		X				X		X			X		X	X	X
Urine collection for ACR1		X	X						X					X	X	X
															X	X
															X	X
Virus serology	X															
PK samples m															X	

Protocol 402-C-1702 Reata Pharmaceuticals, Inc. Confidential

- a Total Screening period should not exceed 6 months.
- b Screen B visit should be no more than 30 days prior to Day 1.
- c Day 1 is the day of administration of the first dose. On Day 1, all procedures should be performed before study drug administration.
- d Patients who terminate from the study prior to the Week 12 study visit should be brought back to the clinic as soon as possible for early termination assessments (i.e., end-of-treatment visit) as well as a follow-up visit 4 weeks later.

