5.3. Assessments

All patients in the study will follow the same visit and assessment schedule. Table 2 lists the overall schedule of assessments for the study. Following randomization on Day 1, patients will be scheduled for assessments during treatment at Weeks 1, 2, 4, 6, 8, and 12, and by telephone contact on Days 3, 10, 21, 31, 38, and 45. Patients will also be scheduled for an in person follow-up visit at Week 16, four weeks after the end of treatment.

Table 2: Schedule of Assessments

Assessment	Screen A ^a	Screen B ^b	Day 1 ^c	Wk 1 (Phone) Day 3±2	Wk 1 Day 7±3	Wk 2 (Phone) Day 10±2	Wk 2 Day 14±3	Wk 3 (Phone) Day 21±2	Wk 4 Day 28±3	Wk 4 (Phone) Day 31±2	Wk 5 (Phone) Day 38±2	Wk 6 Day 42±3	Wk 7 (Phone) Day 45±2	Wk 8 Day 56±3	Wk 12 or EoT ^d Day 84±3	Wk 16 or F/U Day 112±3
Informed consent	X															
Inclusion/ exclusion	X		X ^e													
Demographics and baseline disease characteristics	X															
Concomitant medications	X	X	X	X	X	X	X	X	X	X	X	X	X	X	X	X
Medical history	X															
Height	X															
Weight in clinic/BMI	X		X		X		X		X			X		X	X	X
Weight at home			X	X	X	X	X	X	X	X	X	X	X	X	X	
Dispense weight diary			X				X		X			X		X		
Collect/review weight diary				X	X	X	X	X	X	X	X	X	X	X	X	
ECG	X														X	X
Echocardiogram ^f	X															
Vital sign measurements	X		X		X		X		X			X		X	X	X
Physical exam	X		X		X		X		X			X		X	X	X
Pregnancy test for WOCBP ^g	X	X	X						X					X	X	X
Study drug administration				-----X-----												
Dispense study drug			X				X		X			X		X		
Collect study drug							X		X			X		X	X	
Telephone contact				X		X		X		X	X		X			
Adverse event collection			x ^h	X	X	X	X	X	X	X	X	X	X	X	X	X
Kidney biopsy ⁱ	X															
Fasting C-peptide level ^j	X															

Genetic testing ^k	X															
Assessment	Screen A ^a	Screen B ^b	Day 1 ^c	Wk 1 (Phone) Day 3±2	Wk 1 Day 7±3	Wk 2 (Phone) Day 10±2	Wk 2 Day 14±3	Wk 3 (Phone) Day 21±2	Wk 4 Day 28±3	Wk 4 (Phone) Day 31±2	Wk 5 (Phone) Day 38±2	Wk 6 Day 42±3	Wk 7 (Phone) Day 45±2	Wk 8 Day 56±3	Wk 12 or EoT ^d Day 84±3	Wk 16 or F/U Day 112±3
Clinical chemistry (incl. eGFR)	X	X	X		X		X		X			X		X	X	X
BNP and NT-proBNP	X		X		X		X		X			X		X	X	X
IGF-1 and serum ketones	X		X		X		X		X			X		X	X	X
Hematology	X		X				X		X			X		X	X	X
Urinalysis and microscopy	X		X				X		X			X		X	X	X
Urine collection for ACR ^e		X	X						X					X	X	X
██████████															X	X
██████████															X	X
Virus serology	X															
PK samples ^f															X	

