^a Total Screening period should not exceed 6 months.

^b Screen B visit should be no more than 30 days prior to Day 1.

^c Day 1 is the day of administration of the first dose. **On Day 1, all procedures should be performed before study drug administration.**

^d Patients who terminate from the study prior to the Week 12 study visit should be brought back to the clinic as soon as possible for early termination assessments (*i.e.*, end-of-treatment visit) as well as a follow-up visit 4 weeks later.

^e Screening eligibility procedures do not need to be repeated on Day 1; however, a review of any changes in eligibility criteria should be evaluated prior to Day 1 procedures, and a urine pregnancy test should be performed for WOCBP.

^f An echocardiogram performed at the Screen A visit or within 6 months prior to Day 1 may be used to determine eligibility.

^g A serum pregnancy test will be performed at the Screen A visit for WOCBP or at any point in time if a pregnancy is suspected. All other pregnancy assessments will be urine pregnancy tests.

^h AE assessments on Day 1 should be performed following study drug administration.

ⁱ Only patients enrolling in the IgA nephropathy cohort or the FSGS cohort are required to have a kidney biopsy. Patients with definitive diagnosis of IgA nephropathy or FSGS from previous biopsy will not have a kidney biopsy as part of the study, but must provide diagnosis documentation from previous kidney biopsy for eligibility.

^j Only patients enrolling in the T1D cohort are required to have fasting C-peptide levels assessed. Patients should be instructed to fast prior to study visit.

^k Only patients enrolling in the ADPKD disease cohort are required to have genetic testing. Patients with confirmed PKD1 mutations from previous genetic testing will not have genetic testing performed as part of the study, but must provide documentation of genetic mutation for eligibility.

^l Albumin to creatinine ratio will be measured by first morning void spot urine collection. Appropriate containers for the collection will be provided to the patient at the visit prior to collection.

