12.4. Body Weight

Descriptive statistics for body weight that are collected on the eCRF and change from baseline values will be summarized by time point for each rare CKD cohort. In addition, number and percentage of patients who experience a five-pound (2.3 kilogram) or greater increase in weight will be summarized by time point. Boxplot and line graphs of change from baseline over time for weight will be plotted. Summary tables for body weight will be repeated for the following subgroups:

- Weight change will also be summarized by baseline BMI (>30 and ≤ 30 kg/m²), and
- Baseline age (>18 and ≤ 18).

12.5. 12-lead ECG

Electrocardiogram (ECG) data, such as clinical interpretation of ECGs, ventricular rate and interval assessments of PR, QRS, QT, and QTcF, will be collected on the eCRF. Descriptive statistics for observed values and change from baseline at each time point will be presented for these 12-lead ECG interval assessments by rare CKD cohort. In addition, number and percentage of patients with any abnormal values (i.e., above a pre-specified threshold) will be summarized by time point and overall while on study drug. The pre-specified levels of ECG QTc thresholds are consistent with FDA guidance.

Table 9: Pre-Specified Threshold Levels for ECG Parameters

ECG Parameter	Pre-Specified Level
PR	>200 msec
QTcF	>450 , >480 or >500 msec >30 or >60 msec increase from baseline
Heart rate	<40 , >100 beats/min

Any results that exceed the above levels (provided in the above table) will be flagged in the listing.

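### SAP Table 3 gives the scheduled Week 16 ECG no analysis window, and its Week 12 ECG window has no on-treatment condition

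*SAP*

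**What the plan says.** **Schedule.** Protocol 7.5 (Table 5) and SAP 5.3 (Table 2) agree on three ECGs: Screen A, Week 12 or end of treatment, and Week 16 or follow-up. The last column is headed "Wk 16 or F/U Day 112±3". Patients who terminate the study before Week 12 are to have "early termination assessments (i.e., end-of-treatment visit) as well as a follow-up visit 4 weeks later". Under Protocol 8.5.1, patients who only stop study drug are asked to stay and complete the remaining visits and assessments if possible.

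**Windows.** SAP 7.3 states that "instead of relying solely on visit labels in the clinical database, analysis visits and their windows are defined using Study Day". The Table 3 rows give the target day, the window for all other assessments, and the ECG window. The Week 12 row reads "Week 12 84 71 to 98 2 to 98". The Week 16 row begins "Week 16 112 > 98", and its ECG cell is a dash, the same mark as on visits with no ECG scheduled. The note under the table defines the analysis visit as the result of applying the windows. It limits Week 16 to values after the last dose, and it makes Week 16 the follow-up visit for patients who stopped treatment before Week 12.

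**Analyses.** For ECG, SAP 12.5 plans: "Descriptive statistics for observed values and change from baseline at each time point will be presented for these 12-lead ECG interval assessments". Counts of abnormal values "will be summarized by time point and overall while on study drug". SAP 8.3 defines a Week 16 off-treatment set for evaluating safety off drug. SAP 7.1.3 and 11.1 exclude eGFR values collected after the window of the last dose. No such rule is stated for ECG.

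**The concern.** Change from baseline in 12-lead ECG is a stated safety endpoint (Protocol 6.4, SAP 4.2.3). The Week 16 ECG is the only one scheduled after a planned four weeks off drug. If it has no analysis visit, the by-time-point tables have no off-drug column in which to see whether a QTcF or PR change persisted or receded.

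The second issue concerns the Week 12 column. One window running from Day 2 to Day 98, with no condition on dosing, takes in any ECG in that span. ECGs taken weeks after the last dose could then be averaged with on-drug values, pulling a drug-related change towards zero. Both gaps would leave the programmer to choose a rule with the data in hand.

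**Working it through.** No stated figure needs reproducing. The check applies the ECG column of Table 3 to the days on which ECGs are scheduled.

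**Inputs**

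- ECG windows (SAP Table 3): Day -180 to 1 is Screen A; Day 2 to 98 is Week 12; there are no others.
- Scheduled visits (SAP Table 2): Week 12 at Day 84 ± 3, Week 16 at Day 112 ± 3.
- About 25 patients in each of four cohorts, about 100 in all (SAP 5.1, Protocol 7.2).
- Assumed for illustration: last dose on Day 28; for an early terminator, end-of-treatment visit 7 days later. The follow-up 4 weeks after that visit comes from the schedule.

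**Step 1: scheduled ECGs**

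| Visit | Scheduled days | ECG window | Window for other assessments |
|---|---|---|---|
| Week 12 | 81 to 87 | Week 12 on all 7 days | Week 12 |
| Week 16 | 109 to 115 | none on any of 7 days | Week 16 (> 98) |

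The gap is specific to ECG.

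**Step 2: size**

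Each patient has 2 scheduled post-baseline ECGs, of which 1 has a window. With full attendance the unassigned number is 25 of 2 × 25 = 50 per cohort, or 100 of 2 × 100 = 200 overall.

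If a fraction e of patients terminates early, with follow-up by Day 98, their follow-up ECG lies inside Day 2 to 98. The share with no window becomes (1 - e)/2. The documents give no value for e. Over an assumed 5% to 20%:

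- e = 0.05: 0.95/2 = 47.5%
- e = 0.20: 0.80/2 = 40%

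**Step 3: off-drug ECGs labelled Week 12**

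*Stops drug on Day 28, stays in the study.* The Day 84 ECG is 84 - 28 = 56 days off drug. It falls in the Week 12 window, and no ECG rule removes it. The Table 3 note does not touch it, because it concerns the follow-up visit.

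*Terminates the study, last dose Day 28.* End of treatment is Day 28 + 7 = 35 and follow-up is Day 35 + 28 = 63. Both days lie in Day 2 to 98, as happens whenever the end-of-treatment visit is by Day 98 - 28 = 70. There are two readings:

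- The note moves the follow-up ECG to Week 16. The Day 35 ECG, 7 days off drug, is then the Week 12 value, and the Day 63 ECG is sent to a visit with no ECG window.
- The window governs. Both ECGs are after the last dose, so the rule for several off-treatment values applies. Distances to target are |63 - 84| = 21 and |35 - 84| = 49, so Day 63, which is 63 - 28 = 35 days off drug, is selected.

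The SAP does not say which reading applies. Under either, an ECG taken after the last dose can be summarised as Week 12.

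**The case against.** Several points on the other side have force.

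- **The data are not discarded.** SAP 7 keeps measurements left out of the tables in the listings, and SAP 12.5 flags values beyond the thresholds there. The overall threshold count is limited to time on study drug, so it would rightly omit a Week 16 ECG. A reader might infer that off-drug reversal cannot be shown at all. The documents do not support that: individual values stay visible. What is lost is the tabulation.
- **The Table 3 note deals with early stoppers.** A reader might infer that the plan requires an early stopper's follow-up ECG to be reported as Week 12. It does not. The note is plausibly read as moving that ECG out of Week 12, and the text gives no rule for choosing between one on-treatment and one off-treatment value in the same window. What stands against the note is narrower: the ECG column has no Week 16 window to receive the moved value, and the note does not reach an off-drug Day 84 ECG.
- **The wide Week 12 window may be deliberate.** Day 2 to 98 would catch an end-of-treatment ECG whenever it occurs. That is reasonable for an ECG close to the last dose, but the window sets no limit on the time since dosing.
- **The word 'solely' leaves room for visit labels.** It does, but no rule says when a label overrides a window, and the note sets the analysis visit by window.
- **The stakes are modest.** The primary safety objective is framed at 12 weeks, and no document states an ECG-reversal objective. This limits the severity but leaves the conflict with SAP 12.5 and 8.3 in place.

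**Conclusion.** The point holds as a minor but real inconsistency. A Week 16 ECG taken on schedule has no analysis visit, so the by-time-point ECG summaries at Week 16 and the ECG part of the off-treatment evaluation cannot be produced by the stated rule.

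The size is up to one of two scheduled post-baseline ECGs per patient who attends Week 16. It would be wrong to say without qualification that half of post-baseline ECGs drop out. That share needs full attendance (40% to 47.5% under the assumed early-termination range), and the loss is from summaries only.

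Separately, an off-drug ECG can enter the Week 12 summary. The clearest case is the patient who stops drug and stays in the study, which depends on no tie-breaking rule. How much this would dilute the Week 12 results cannot be sized, because the documents give no discontinuation rate. The primary efficacy analysis is unaffected.

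**What to change.** Three edits to the SAP before database lock:

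1. In the ECG column of Table 3, set Week 16 to '> 98', after the last dose, as for all other assessments. This assigns all seven scheduled days (109 to 115).
2. State that the existing note, under which an early stopper's follow-up visit counts as Week 16, applies to ECGs whatever the Study Day.
3. Apply to the Week 12 ECG summary the last-dose exclusion already used for eGFR. The wording should point to the windows in the column for all other assessments. The ECG column's own window containing a last dose between Days 2 and 98 is Day 2 to 98, so a literal transfer would exclude nothing within it. Read this way, a last dose on Day 28 falls in the Week 4 window (Day 22 to 35): an ECG on Day 35 stays, and ECGs on Days 63 and 84 do not enter Week 12.

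The first edit alone would not keep off-drug ECGs out of Week 12, so the third is needed as well. The cost is one table cell, two sentences and minor programming, with no new visits or data. The downside is slightly fewer ECGs in the Week 12 summary. An end-of-treatment ECG that falls just past the window of the last dose would be left out too, though it would still be listed.

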8. ANALYSIS SETS

The analysis sets defined below will be defined for each rare CKD cohort: CKD associated with T1D, IgAN, FSGS, and ADPKD.

8.1. Safety Analysis Set

Safety analysis set is defined as all patients who received any amount of study drug. The safety analysis set will be used for evaluation of safety variables.

8.2. ITT Analysis Set

The intent-to-treat analysis set is defined as all enrolled patients.

8.3. Off-Treatment Analysis Sets

The Week 16 off-treatment analysis set is defined as all randomized patients who were dosing compliant through Week 12 as defined by:

- Still taking study medication at the Week 12 in-person visit; and
- Had a Week 16 assessment.

The off-treatment analysis sets will be used for evaluation of off-treatment safety at Week 16.

8.4. Pharmacokinetics Analysis Set

Pharmacokinetics analysis set is defined as all patients who received any amount of study drug and had at least one bardoxolone methyl plasma concentration measurement. The PK analysis set will be used for evaluation of pharmacokinetics.

9. STUDY POPULATION

9.1. Patient Disposition

Enrollment and disposition will be summarized by rare CKD cohort. A patient will be defined as enrolled if they sign the informed consent form. The patient disposition summary will include the number of patients who:

- enrolled in the study
- are in the safety analysis set
- are in the ITT analysis set
- are in the Week 16 off-treatment analysis set
- completed study treatment

- prematurely discontinued study treatment
- completed study visits
- prematurely terminated from the study.

The disposition summary will also include the primary reason for withdrawal from the study.

Patients who completed study treatment are defined as those who received treatment through the Week 12 visit. Patients who completed study visits are defined as those who completed the Week 16 visit. A listing of disposition will be provided for all enrolled patients, including patient source.

9.2. Protocol Deviations

Where available, protocol deviations will be listed by deviation category (e.g., eligibility criteria, out of window visit, serious adverse event (SAE) reporting, study procedures, treatment procedures). All deviations, including major protocol deviations that could potentially affect the efficacy or safety conclusions of the study, will be identified prior to database lock. Major protocol deviations will be listed in a data listing.

9.3. Demographics and Baseline Characteristics

Demographics and baseline characteristics will be summarized by rare CKD cohort for the safety analysis set. Demographic characteristics will include age, gender, race, and ethnicity. Baseline ACR will be summarized by baseline ACR values, not the stratification cohort to which a patient was randomized. The baseline characteristics include:

- Baseline weight,
- Height,
- Body mass index (BMI), and BMI category: < 30 , ≥ 30 ,
- Baseline values of eGFR, baseline CKD stage (Stage 3: eGFR 30 to < 60 ; Stage 2: eGFR ≥ 60 to < 90 ; Stage 1: eGFR ≥ 90),
- Baseline serum creatinine,
- Baseline ACR,
- Baseline ACR status (ACR ≤ 300 mg/g; 300 mg/g $<$ ACR ≤ 1000 mg/g; ACR $>$ 1000 mg/g),
- Age of the diagnosis (T1D cohort only)
- C-peptide level (T1D cohort only),
- Prescribed a stable dose of insulin (T1D cohort only), and

- Baseline Angiotensin converting enzyme (ACE)-inhibitor and Angiotensin II receptor blocker (ARB) use:
 - Only ACEi treatment;
 - Only ARB treatment;
 - ACEi and ARB treatment
 - No ACEi or ARB treatment.

The above information will be listed by patient.

9.4. Medical History

Medical history will be mapped to preferred terms (PT) and system organ classes (SOC) using the Medical Dictionary for Regulatory Activities (MedDRA[®]) Dictionary (version 14.1). Medical history items will be summarized by MedDRA SOC, cohort, and PT and patient listing will be provided.

10. STUDY DRUG AND OTHER MEDICATIONS

10.1. Prior and Concomitant Medications

Prior and concomitant medication verbatim terms on eCRFs will be mapped to Anatomical/Therapeutic/Chemical (ATC) class and preferred names using the World Health Organization Drug Dictionary (WHO DD) (Enhanced version, September 2011, B2 format).

A prior medication is any medication that is taken and stopped prior to the first dose of study drug. Medications are stopped on the date of first study drug administration are prior medications. A concomitant medication is any medication taken at the time of first study treatment or a medication that was started after the start of study drug dosing. Specifically, concomitant medications are medications

- that are continued from screening and continued after the first study drug dosing, or
- that have start dates or stop dates within the treatment period.

Prior and concomitant medications will be summarized within each rare chronic kidney disease cohort by WHO DD ATC class and preferred name. These summaries will present the number and percentage of patients using each medication. Patients may have more than one medication per ATC class and preferred name. At each level of patient summarization, a patient is counted once if he/she reported one or more medications at that level. Each summary will be ordered by descending order of incidence of ATC class and preferred name within each ATC class.

In addition, patients who take excluded medications (defined in the Protocol Section 9.3.1) during the study will be listed.

